### 8.3.6 Clinical Laboratory Assessments

Refer to Appendix 2 for the list of clinical laboratory tests to be performed and to the SoA for the timing and frequency.

All protocol-required laboratory assessments, as defined in Appendix 2, must be conducted in accordance with the laboratory manual and Section 1.3.

If laboratory values from nonprotocol-specified laboratory assessments performed at the institution's local laboratory require a change in study participant management or are considered clinically significant by the investigator (eg, SAE or AE or dose modification), then the results must be recorded in the appropriate CRF (eg, SLAB).

For any laboratory tests with values considered clinically significantly abnormal during participation in the study, every attempt should be made to perform repeat assessments until the values return to normal or baseline or if a new baseline is established as determined by the investigator.

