# 10.3 Appendix 3: Adverse Events: Definitions and Procedures for Recording, Evaluating, Follow-up, and Reporting

#### 10.3.1 Definition of AE

#### AE definition

- An AE is any untoward medical occurrence in a clinical study participant, temporally associated with the use of study intervention, whether or not considered related to the study intervention.
- NOTE: An AE can therefore be any unfavorable and unintended sign (including an abnormal laboratory finding), symptom, or disease (new or exacerbated) temporally associated with the use of a study intervention.
- NOTE: For purposes of AE definition, study intervention (also referred to as Sponsor's product) includes any pharmaceutical product, biological product, vaccine, diagnostic agent, or protocol specified procedure whether investigational or marketed (including placebo, active comparator product, or run-in intervention), manufactured by, licensed by, provided by, or distributed by the Sponsor for human use in this study.

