#### **Events meeting the AE definition**

- Any abnormal laboratory test results (hematology, clinical chemistry, or urinalysis) or other safety assessments (eg, ECG, radiological scans, vital signs measurements), including those that worsen from baseline, considered clinically significant in the medical and scientific judgment of the investigator.
- Exacerbation of a chronic or intermittent pre-existing condition including either an increase in frequency and/or intensity of the condition.
- New conditions detected or diagnosed after study intervention administration even though it may have been present before the start of the study.
- Signs, symptoms, or the clinical sequelae of a suspected drug-drug interaction.
- Signs, symptoms, or the clinical sequelae of a suspected overdose of either study intervention or a concomitant medication.
- For all reports of overdose (whether accidental or intentional) with an associated AE, the AE term should reflect the clinical symptoms or abnormal test result. An overdose without any associated clinical symptoms or abnormal laboratory results is reported using the terminology "accidental or intentional overdose without adverse effect."

Any new cancer or progression of existing cancer.

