# 3 ANALYTICAL AND METHODOLOGICAL DETAILS

# 3.1 Statistical Analysis Plan Summary

Key elements of the statistical analysis plan are summarized below; the comprehensive plan is provided in Sections 3.2 through 3.12.

Study Design Overview  Intervention Assignment	A Phase 3, Multicenter, Randomized, Double-blind, Active Comparator-controlled Study to Evaluate the Safety, Tolerability, and Immunogenicity of V114 Followed by Administration of PNEUMOVAX TM 23 Eight Weeks Later in Children Infected with Human Immunodeficiency Virus (HIV) (PNEU–WAY PED)  Participants will be randomly assigned in a 1:1 ratio to V114 or		
	Prevnar 13 ™ , respectively.		
Analysis Populations	Immunogenicity: Per-Protocol (PP) Safety: All Participants as Treated (APaT)		
Primary Endpoint(s)	
 
Immunogenicity:         
 
Anti-PnPs serotype-specific IgG GMCs for the 15 serotypes contained in V114 at 30 days postvaccination with V114 or Prevnar 13TM
 
 
 
Safety:         
 
Proportion of participants with solicited injection-site AEs (redness/erythema, swelling, tenderness/pain, and hard lump/induration) from Day 1 through Day 14 following V114 or Prevnar 13TM
 
Proportion of participants with solicited systemic AEs (muscle pain/myalgia, joint pain/arthralgia, headache, tiredness/fatigue, and hives or welts/urticaria) from Day 1 through Day 14 following V114 or Prevnar 13TM
 
Proportion of participants with vaccine-related SAEs through completion of study participation
 
 
 
		
Key Secondary Endpoints	
 
Immunogenicity:
 
Anti-PnPs serotype-specific OPA GMTs for the 15 serotypes contained in V114 at 30 days postvaccination with V114 or Prevnar 13TM
 
Anti-PnPs serotype-specific OPA GMTs and IgG GMCs at 30 days postvaccination with PNEUMOVAXTM23 (Week 12)
 
		

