#### 3.6.2 **Statistical Methods for Safety Analyses**

Safety and tolerability will be assessed by clinical review of all relevant parameters including AEs and postvaccination temperature measurements.

The analysis strategy for safety parameters following each vaccination is summarized in **Table 3.** The proportion of participants with solicited injection-site AEs (redness/erythema, swelling, tenderness/pain, and hard lump/induration from Day 1 to Day 14 postvaccination) and solicited systemic AEs (muscle pain/myalgia, joint pain/arthralgia, headache, tiredness/fatigue, and hives or welts/urticaria from Day 1 to Day 14 postvaccination) will be provided along with the corresponding within-group 95% CIs (based on the exact binomial method proposed by Clopper and Pearson [Clopper, C. J. 1934]). In addition, the broad AE categories consisting of the proportion of participants with any AE, a vaccine-related AE, a SAE, an AE which is both vaccine-related and serious, discontinuation due to an AE, and death will be summarized in the same manner. The proportion of participants with maximum temperature measurements meeting the Brighton Collaboration cut points (from Day 1 through Day 7) will also be provided along with the corresponding within-group 95% CIs. Point estimates by vaccination group will be provided for all other safety parameters (specific AE terms and system organ class terms).

The analysis of safety parameters will be evaluated at 2 separate time points: (1) following administration of V114 or Prevnar 13TM and (2) following administration of PNEUMOVAXTM23. Descriptive summaries of AEs following administration of V114 or Prevnar 13TM will include nonserious AEs within 14 days of vaccination and SAEs occurring Day 1 through Week 8 (prior to vaccination with PPV23). Descriptive summaries of AEs following administration of PNEUMOVAXTM23 will include nonserious AEs within 14 days of vaccination and SAEs occurring Week 8 (following vaccination with PPV23) through Month 6 (completion of study participation).

Table 3 Analysis Strategy for Safety Parameters Following Each Vaccination

Safety Endpoint	Within-Group 95% CI	Descriptive Statistics
Injection-site redness/erythema (Days 1 to 14) †	X	X
Injection-site swelling (Days 1 to 14)†	X	X
Injection-site tenderness/pain (Days 1 to 14) $^{\dagger}$	X	X
Injection-site hard lump/induration (Days 1 to $14$ ) †	X	X

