Muscle pain/myalgia (Days 1 to 14) †	X	X
Joint pain/arthralgia (Days 1 to 14) †	X	X
Headache (Days 1 to 14) †	X	X
Tiredness/fatigue (Days 1 to 14) †	X	X
Hives or welts/urticaria (Days 1 to 14)†	X	X
Any AE ‡	X	X
Any vaccine-related AE ‡	X	X
Any SAE ‡	X	X
Any vaccine-related SAE ‡	X	X
Discontinuation due to AE ‡	X	X
Death ‡	X	X
Maximum temperature measurements meeting the Brighton Collaboration cut points (Days 1 to 7)	X	X
Specific AEs by SOCs and PT		X

† Includes solicited events only.

Safety analyses will be based on the observed data (ie, with no imputation of missing data).

<sup>‡ These endpoints are broad adverse event categories. For example, descriptive statistics for the safety endpoint of "Any AE" will provide the number and percentage of participants with at least 1 AE.

AE = adverse event; CI = confidence interval; PT = preferred term; SAE = serious adverse event; SOC = system organ class; X = results will be provided.

Laboratory AEs will not be reported in summary tables as laboratory safety testing is not performed as part of the study and, therefore, any such AEs would only be reported spontaneously. A listing of laboratory AEs will be provided.

A supportive analysis summarizing the proportion of participants reporting each of the solicited complaints on the VRC will be conducted in support of the primary safety analyses that are based on solicited AEs. This supportive analysis will use the methodology specified in **Table 3** for solicited AEs. The analysis will be conducted on the subset of the APaT population who entered solicited complaints data on the VRC.

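### The sSAP keeps all laboratory AEs out of the summary tables without excepting serious or vaccine-related ones, which conflicts with the primary vaccine-related SAE endpoint and can bias its count low

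*Combined protocol and SAP*

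**What the plan says.** **The exclusion.** sSAP 3.6.2, after Table 3, states: "Laboratory AEs will not be reported in summary tables as laboratory safety testing is not performed as part of the study". The reason added is that such events would reach the sponsor only by spontaneous report. In place of a summary, "A listing of laboratory AEs will be provided". Seriousness, relatedness, death and discontinuation are not mentioned as exceptions.

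**The endpoint.** sSAP 3.1 names as a primary safety endpoint: "Proportion of participants with vaccine-related SAEs through completion of study participation". sSAP 3.4.2 repeats the SAE categories. Neither section sets laboratory events apart.

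**How the endpoint is summarised.** sSAP 3.6.2 gives exact intervals for solicited AEs, "based on the exact binomial method proposed by Clopper and Pearson". It then says that the broad categories, including "a SAE, an AE which is both vaccine-related and serious, discontinuation due to an AE, and death will be summarized in the same manner". Table 3 marks each of these rows for a within-group 95% CI, and its footnotes do not exclude laboratory events.

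**What counts as an AE.** Protocol 10.3.1 says: "An AE can therefore be any unfavorable and unintended sign (including an abnormal laboratory finding), symptom, or disease". The same section counts laboratory abnormalities judged clinically significant as AEs. Protocol 8.3.6 requires local laboratory results to be recorded when the investigator considers them clinically significant, and gives SAEs and AEs as examples.

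**Where the rule came from.** The protocol's own safety methods (9.6.2 and Table 5) contain no laboratory exclusion. sSAP 2.1 lists it as an added analysis detail, and sSAP 1 describes the sSAP's changes as not principal in nature.

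**The concern.** An event can satisfy the definition of the primary endpoint and still be barred from the table that estimates it. The rationale explains caution about rates of minor laboratory findings: without scheduled testing, their frequency depends on who happens to be tested. It does not carry over to serious events. Protocol 8.4.1 requires every SAE to be reported throughout participation, and the Month 6 telephone contact (8.1.11) asks about SAEs. Other unsolicited SAEs are tabulated although no scheduled test looks for them.

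At stake is the numerator of a primary safety proportion whose expected count is very small, so one participant can change the reported result from no events to some. The rows for any AE, any vaccine-related AE, any SAE, discontinuation due to an AE, and death are exposed in the same way.

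**Working it through.** **1. The plan's own figures.** Inputs from sSAP 3.9.2: n = 200 in the V114 group, all evaluable for safety.

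- Chance of at least one SAE = 1 − (1 − p)^200. At p = 0.8% this is 79.9% (plan: 80%). At p = 0.35% it is 50.4%, and at 1/289 it is 50.0% (plan: 50%).
- Upper limit with no SAE = 1 − 0.025^(1/200) = 1.828%, or about 1 in 54.7 (plan: below 1.82%, 1 in 55). The difference is rounding, since 1/55 = 1.818%.

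These figures reproduce. They concern any SAE and are planning statements; the method carries over to any binomial safety row.

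**2. What the text does to one participant.** Suppose one V114 participant has a single vaccine-related SAE and it is recorded as a laboratory AE.

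- Under the endpoint definition (sSAP 3.1) the participant counts.
- Under the laboratory paragraph (sSAP 3.6.2) the event is listed and not tabulated, so the participant does not count.

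**3. Size of that difference.** Clopper-Pearson 95% limits for x of n are the 2.5% quantile of Beta(x, n − x + 1), taken as 0 when x = 0, and the 97.5% quantile of Beta(x + 1, n − x).

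| Participants counted | Proportion | 95% CI |
|---|---|---|
| 0/200 | 0% | 0 to 1.83% |
| 1/200 | 0.5% | 0.01% to 2.75% |
| 2/200 | 1.0% | 0.12% to 3.57% |
| 3/200 | 1.5% | 0.31% to 4.32% |

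Ratio of successive upper limits: 2.754/1.828 = 1.51 for the first participant, 3.565/2.754 = 1.29 for the second and 4.321/3.565 = 1.21 for the third. The effect is largest for a first event and shrinks after that.

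**4. Sensitivity of the *Any SAE* row.** The documents give no share of SAEs that would be laboratory events, so the share f is an assumption. Chance of at least one tabulated SAE = 1 − (1 − 0.008(1 − f))^200.

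| Assumed f | Chance of at least one tabulated SAE |
|---|---|
| 0 | 79.9% |
| 5% | 78.3% |
| 10% | 76.4% |
| 20% | 72.3% |

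**5. Direction.** The rule removes participants from numerators and never adds any, so any error in these proportions is downward.

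**The case against.** The strongest reply is that the affected set is narrow. To change the primary count, an event must be recorded as a laboratory AE, meet a seriousness criterion, be judged vaccine-related and be that participant's only such SAE. No safety laboratory testing follows vaccination: HIV serology, CD4+ count and HIV RNA are drawn only at screening. Protocol 10.3.4 asks investigators to record a diagnosis in preference to signs, so many serious events might never be classed as laboratory AEs. The rule is disclosed, applies to both groups and leaves the events in a listing. The DMC still reviews safety, and no hypothesis test depends on the count.

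Most of this stands, and it limits the size of the problem. It does not remove the conflict. A listing shows the event but supplies neither the proportion nor its interval. DMC review and a descriptive design do not correct a reported numerator. The diagnosis argument cuts both ways: laboratory AE is undefined, and protocol 10.3.2 names blood dyscrasias as important medical events, so it is unclear whether a cytopenia falls under the rule.

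A reader might infer more than the documents support:

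- *That the primary result is biased low by the rule itself.* It is biased only if a qualifying event occurs.
- *That every omitted event raises the upper limit 1.5-fold.* The endpoint counts participants, and that ratio applies only to the first.
- *That the 1.82% bound in sSAP 3.9.2 is the vaccine-related SAE result.* It is a planning bound for any SAE.
- *That HIV-related findings from routine care, such as a CD4 fall, could enter no summary.* That depends on how they are recorded. Nonserious ones would in any case be collected only through Day 14 after each vaccination, apart from the interval between randomization and first vaccination.

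**Conclusion.** The point holds as a conflict within the sSAP. The laboratory paragraph is unconditional, while the primary vaccine-related SAE endpoint and the Table 3 broad-category rows admit laboratory events. Read literally, the paragraph can produce a wrong primary count, and only in the low direction. For a first affected participant, with 200 evaluable in the V114 group, 0% (0 to 1.83%) would be reported where 0.5% (0.01% to 2.75%) is correct.

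This rests on reading the paragraph as written. The sponsor may have meant only nonserious laboratory AEs, but nothing in the documents says so. The events are probably rare and their number cannot be estimated from the documents. The endpoint definition itself has not been changed, and the trial's design is not in question. The gap should be closed because it touches a primary safety endpoint and costs almost nothing to repair.

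**What to change.** Amend the laboratory paragraph in sSAP 3.6.2 so that it says the following:

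- Laboratory AEs that are serious, vaccine-related, fatal or lead to discontinuation count in every Table 3 broad AE category that applies, including *Any AE*, and in the summary by system organ class and preferred term.
- Only the remaining laboratory AEs, which are nonserious, judged unrelated and did not lead to discontinuation, are shown in the listing alone.
- Laboratory AE is defined, with a statement of how it differs from a recorded diagnosis that rests on laboratory findings.

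How to display the remaining events is the sponsor's choice and needs no new summary row. The change is confined to this paragraph and the tables that follow it. If serious laboratory events were always meant to be counted, it alters no result. If not, reported AE or SAE rates may be slightly less favourable.

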### 3.6.3 **Demographic and Baseline Characteristics**

The comparability of the vaccination groups for each relevant demographic and baseline characteristic will be assessed using summary tables. No statistical hypothesis tests will be performed on these characteristics. The number and percentage of participants screened and randomized and the primary reasons for screening failure and discontinuation will be displayed. Demographic variables (eg, age, race, and gender), baseline characteristics, and prior and concomitant vaccinations and therapies will be summarized by vaccination group either by descriptive statistics or categorical tables.

#### 3.7 **Interim Analyses**

A periodic review of safety and tolerability data across the V114 Phase 3 pediatric program will be conducted by an independent, unblinded, external DMC. A description of the structure and function of the DMC, along with the timing and content of the safety reviews will be outlined in the DMC Charter. Information regarding the composition of the DMC is provided in Appendix 1 of the protocol. There are no plans to conduct an interim analysis of unblinded immunogenicity data in this study. However, unblinded immunogenicity data will be made available to the DMC upon request to enable a benefit-risk assessment.

The DMC will serve as the primary reviewer of the results of the ongoing safety reviews and will make recommendations for discontinuation of the study or protocol modifications to an executive committee of the Sponsor (see Appendix 1 of the protocol for details on the Committees Structure for this study). If the DMC recommends modifications to the design of the protocol or discontinuation of the study, this Executive Oversight Committee (EOC) of the Sponsor (and potentially other limited Sponsor personnel) may be unblinded to results at the intervention level to act on these recommendations. The extent to which individuals are unblinded with respect to results of ongoing safety reviews will be documented by the external unblinded statistician. Additional logistical details will be provided in the DMC Charter.

Study enrollment is likely to be ongoing at the time of external DMC review. Blinding to intervention assignment will be maintained at all investigational sites. Participant-level unblinding will be restricted to an external unblinded statistician performing ongoing safety reviews. Intervention-level ongoing safety reviews will be provided by the external unblinded statistician to the DMC. Prior to final study unblinding, the external unblinded

statistician will not be involved in any discussions regarding modifications to the protocol, statistical methods, identification of protocol deviations, or data validation efforts after the safety review.

### 3.8 **Multiplicity**

No adjustment will be made for multiplicity.

### 3.9 Sample Size and Power Calculations

#### 3.9.1 Sample Size and Power for Immunogenicity Analyses

This is a descriptive study. The planned sample size is 400 participants. Participants are to be randomly assigned in 1:1 ratio to V114 or Prevnar 13TM. It is assumed that approximately 160 participants per vaccination group will be evaluable for PP immunogenicity analyses at Day 30 (based on an 80% evaluability rate).

The width of the within-group 95% CIs for the serotype-specific IgG GMCs depends on the sample size, variability of the natural log concentrations, and the magnitude of the IgG GMC. In **Table 4**, 95% CIs for various hypothetical IgG GMCs at 30 days postvaccination with V114 or Prevnar 13™ and various hypothetical standard deviation estimates for the natural log concentrations are displayed.

Table 4 Within-Group 95% CIs for Varying Hypothetical IgG GMCs and Varying Standard Deviations With 160 Evaluable Participants in Each Vaccination Group

Standard Deviation of Natural Log	Observed Serotype-specific IgG GMC †			
Concentrations †	1	5	10	
1.0	(0.86, 1.17)	(4.28, 5.84)	(8.55, 11.69)	
1.5	(0.79, 1.26)	(3.96, 6.32)	(7.91, 12.64)	
2.0	(0.73, 1.37)	(3.66, 6.83)	(7.32, 13.67)	

† The estimates of the standard deviation and IgG GMC ratio are representative of those observed in a previous MSD study.

### 3.9.2 Sample Size and Power for Safety Analyses

The sample size was selected to achieve a reasonably sized safety database in this population exposed to V114. The probability of observing at least 1 SAE in this study depends on the number of participants vaccinated and the underlying percentage of participants with a SAE in the study population. Calculations below assume that 100% of the randomized participants will be evaluable for safety analyses. There is an 80% chance of observing at least 1 SAE among 200 participants in the V114 group if the underlying incidence of a SAE is 0.8% (1 of every 125 participants receiving the vaccine). There is a 50% chance of observing at least 1 SAE among 200 participants in the V114 group if the underlying incidence of a SAE is

CI = confidence interval; GMC = geometric mean concentration.

0.35% (1 of every 289 participants receiving the vaccine). If no SAEs are observed among the 200 participants in the V114 group, this study will provide 97.5% confidence that the underlying percentage of participants with a SAE is <1.82% (1 in every 55 participants) in the V114 group.

#### 3.10 **Subgroup Analyses**

Serotype-specific IgG GMCs and their corresponding within-group 95% CIs at Day 30 will be calculated for each subgroup (eg, CD4+ T-cell count, sex, age, race, prior vaccination of PCV) within each vaccination group. Analyses will only be performed for each subgroup with  $\geq$ 5% of the total number of randomized participants in each vaccination group. In addition, a summary of AEs and a summary of solicited AEs following PCV will be provided for each subgroup (point estimates only) with  $\geq 5\%$  of the total number of randomized participants in each vaccination group.

The following subgroups are planned for evaluation:

- Age category (6 to 9 years, 10 to 14 years, 15 to 17 years)
- Ethnicity (Hispanic or Latino, Not Hispanic or Latino)
- Race (American Indian or Alaska Native, Asian, Black or African American, Multiple, Native Hawaiian or Other Pacific Islander, White)
- Sex (Female, Male)
- CD4+ T-cell count category ( $\geq 200$  to < 500 cells/ $\mu$ L,  $\geq 500$  cells/ $\mu$ L)
- Prior PCV status (PCV Naïve, Receipt of Prior PCV)
- Prior PPV23 status (PPV23 Naïve, Receipt of Prior PPV23)

